15.6. Subject Death

All subject deaths must be reported by the Investigator to Medtronic on an adverse event eCRF (AE with outcome of death) as soon as possible after the Investigator first learns of the death. There should be one AE with the outcome of death.

A copy of the death certificate, if available and allowed by state/local law, should be sent to the Medtronic clinical study team. When a death occurs in a hospital, a copy of the death summary report and all relevant hospital records should be sent to the Medtronic clinical study team, if available. If an autopsy is conducted, the autopsy report should also be sent to the Medtronic clinical study team if available and allowed by

state/local law. When the death occurs at a remote center, it is the investigative center's responsibility to attempt retrieval of information about the death. In summary, the following data will be collected:

- Date of death
- Detailed description of death
- Cause of death
- Relatedness to device and/or procedure
- Death summary/hospital records (if available and allowed by state/local law)
- Autopsy report (if available and allowed by state/local law)
- Death certificate (if available and/or allowed by state/local law)

15.6.1. Death Classification and Reporting

Sufficient information will be required in order to properly classify the subject's death. The Investigator shall classify each subject death per the following definitions:

- Cardiac Death: A death directly related to the electrical or mechanical dysfunction of the heart.
- Sudden Cardiac Death (SCD): Natural death due to cardiac causes, indicated by abrupt loss of consciousness within one hour of the onset of acute symptoms; preexisting heart disease may have been known to be present, but the time and mode of death are unexpected. If time of onset cannot be determined, SCD will alternatively be defined as any unexpected cardiac death occurring out of the hospital or in the emergency room as dead on arrival.
- Non-sudden Cardiac Death: All cardiac deaths that are not classified as sudden deaths, including all cardiac deaths of hospitalized subjects on inotropic support.
- Non-cardiac Death: A death not classified as a cardiac death.
- Unknown Classification: Unknown death classification is intended for use only when there is insufficient or inadequate information to classify the death.

The CEC will review deaths and provide a final adjudication of the primary cause of death and cardiac classification.

Regulatory reporting of Subject Deaths will be completed according to local regulatory requirements.

15.7. Product Complaint Reporting

In geographies where devices are market-released, product complaint reporting is applicable. This includes when an AE is related to a market-released device during the study. The reporting of product complaints is not part of the clinical study and should be done in addition to the Adverse Event reporting requirements. Refer to local regulations for reporting requirements.

Product Complaint: Any written, electronic or oral communication that alleges deficiencies related to the identity, quality, durability, reliability, safety, effectiveness or performance of a medical device that has been placed on the market.

It is the responsibility of the Investigator to report all product complaint(s) associated with a medical device distributed by Medtronic, regardless whether they are related to intended use, misuse or abuse of the product. Reporting must be done immediately and via the regular channels for market-released products.

Medtronic will notify the regulatory authorities (e.g. FDA) as applicable for the following incidents immediately upon learning of them:

- Any malfunction or deterioration in the characteristics and/or performance of a device, as well as any inadequacy in the labeling or instructions for use which led or might have led to the death or serious deterioration in the state of health of a patient, user, or other person.
- Any technical or medical reason resulting in withdrawal of a device from the market by the manufacturer.
- A serious deterioration in the state of health includes:
 - Life-threatening illness or injury
 - Permanent impairment of a body function or permanent damage to a body structure
 - A condition necessitating medical or surgical intervention to prevent permanent impairment of a body function or permanent damage to a body structure

The Investigator and Medtronic must abide by the reporting requirements shown in Section 19.5.

16. Data Review Committees

At regular intervals, an independent Clinical Events Committee (CEC) will review and adjudicate, at a minimum, all system (cryoablation and [REDACTED]) related and all procedure related adverse events, as well as all deaths for subjects participating in the study.

The CEC will consist of a minimum of three (3) non-Medtronic employed physicians that are not participating Investigators for the study, including a CEC chairperson.

Medtronic personnel may facilitate and participate in a CEC meeting but will be non-voting members.

For adverse events and deaths reviewed by the CEC, Medtronic will provide the CEC with the Investigator's description and classification. The CEC is responsible for reviewing the Investigator's assessment and supportive documentation (when available), reviewing applicable definitions, and determining final classifications for all adjudication parameters. Associated imaging studies (i.e. CT, MRI, x-ray, etc.) may be requested, if available, for all serious adverse events with possible relatedness to the system or procedure listed in Section 18.3.2 to support adjudication. Additionally, the CEC will provide an adjudication of the death classification for all reported deaths including primary cause of death and cardiac classification.

If the CEC disagrees with the Investigator's classification of the event, the rationale will be provided to the Investigator. If the Investigator agrees with the CEC's adjudication, the eCRF documenting the event will be updated accordingly.

If the Investigator does not agree with the CEC's adjudication classification, both determinations will be provided within the final report; however, the CEC's adjudication will be used for data analysis. The disagreement will also be included in reporting to IRB/MECs and regulatory authorities, if required.

17. Statistical Design and Methods

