15.1. Adverse Event and Device Deficiency Definitions

Where the definition indicates “device”, it refers to any device used in the study. This might be the catheter, or any other component of the system under investigation, or any market-released component of the system.

Table 9: Adverse Event and Device Deficiency Definitions

General	
Adverse Event (AE)	
Any untoward medical occurrence, unintended disease or injury, or untoward clinical signs (including abnormal laboratory findings) in subjects, users or other persons, whether or not related to the investigational medical device
 
NOTE 1: This definition includes events related to the investigational medical device or the comparator. NOTE 2: This definition includes events related to the procedures involved. NOTE 3: For users or other persons, this definition is restricted to events related to investigational medical devices. (ISO 14155:2011, 3.2)

Adverse Device Effect (ADE)	
Adverse event related to the use of an investigational medical device
 
NOTE 1: This definition includes adverse events resulting from insufficient or inadequate instructions for use, deployment, implantation, installation, or operation, or any malfunction of the investigational medical device. NOTE 2: This definition includes any event resulting from an error use or from intentional misuse of the investigational medical device. (ISO 14155:2011, 3.1)

Device Deficiency (DD)	
Inadequacy of a medical device with respect to its identity, quality, durability, reliability, safety or performance.
 
NOTE: Device deficiencies include malfunctions, use errors and inadequate labeling (ISO 14155:2011, 3.15)

Relatedness	
Procedure related	An Adverse Event directly related to any portion of the procedure that encompasses cryoablation.
Cryoablation system related	An Adverse Event that results from the presence or performance (intended or otherwise) of the cryoablation system (including the Arctic Front Advance, Freezor MAX, FlexCath Sheath, Achieve Mapping Catheter, CryoConsole, Manual Retraction Kit)

STOP Persistent AF Clinical Investigation Plan

Version 6.0, 01DEC2017 Page 52 of 128

[REDACTED]	[REDACTED]
Cardiovascular related	An Adverse Event relating to the heart and the blood vessels or the circulation.
Seriousness	

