15.2. Adverse Events

For the purposes of the study, the following Adverse Events will be collected starting at the time of signing the PIC Form through the duration of the subject’s participation in the study:

- All procedure related AEs
- All system related AEs (cryoablation and [REDACTED])
- All cardiovascular related AEs
- All Serious Adverse Events (SAEs), regardless of relatedness

Reporting of these events to Medtronic will occur on an Adverse Event (AE) eCRF, including a description of AE, date of onset of AE, date of awareness of center, treatment, resolution, assessment of both the seriousness and the relatedness to the investigational device. Each AE must be recorded on a separate AE eCRF. Exceptions include:

- Documented pre-existing conditions are not considered AEs unless the nature or severity of the condition has worsened. Additionally, arrhythmia episodes that are not new or worsening conditions and for which no action is taken are not reportable as AEs.
- Unavoidable Adverse Events, listed in Table 9 need not be reported unless the adverse event worsens or is present outside the stated timeframe after the ablation procedure.
- Cardioversions (DC or Drug) for recurrent symptomatic atrial fibrillation and other atrial arrhythmias are not considered serious adverse events

Subject deaths are also required to be reported. Refer to section 15.6 for Subject Death collection and reporting requirements.

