15.5. Reporting of Adverse Events and Device Deficiencies

All reported adverse events and device deficiencies will be reviewed by a Medtronic representative. AEs will be classified according to the definitions provided.

Upon receipt of adverse events at Medtronic, a Medtronic representative will review the adverse event/device deficiency for completeness and accuracy and when necessary will request clarification and/or additional information from the Investigator. Medtronic will utilize MedDRA, the Medical Dictionary for Regulatory Activities, to assign a MedDRA term for each adverse event based on the information provided by the Investigator.

Regulatory reporting of AEs and device deficiencies that could have led to a SADE will be completed according to local regulatory requirements. Refer to Section 19.5 for a list of required Investigator and Medtronic reporting requirements and timeframes. It is the responsibility of the Investigator to abide by any additional AE reporting requirements stipulated by the IRB/MEC responsible for oversight of the study.

For a list of Foreseeable Adverse Event List (FAL), refer to Appendix G. This is a list of adverse events related to the Arctic Front Advance CryoAblation Catheter or procedure that have been observed in previous studies and may be experienced by subjected. This list may help to assess if an adverse event is unexpected in nature.

For emergency contact regarding a SAE, contact a clinical study representative immediately (refer to the study sponsor per the sponsor contact information).

Adverse Events and Deaths will be classified according to the standard definitions as outlined below:

Table 10: Adverse Event Classification Responsibilities

What is classified?	Who classifies?	Classification Parameters
Relatedness	Investigator	Cryoablation procedure related, Cryoablation system related, ██████████, Cardiovascular related
	Sponsor	Cryoablation procedure related, Cryoablation system related, ██████████
Seriousness	Investigator	SAE
	Sponsor	SAE, UADE/USADE, Device Deficiency with SADE potential
Diagnosis	Investigator	Based on presenting signs and symptoms and other supporting data
	Sponsor	MedDRA term assigned based on the data provided by Investigator
Death Classification	Investigator	Sudden Cardiac, Non-sudden Cardiac, Non-Cardiac, Unknown

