6.2. General Methodology

6.2.1. Overview

This study follows patients with drug refractory symptomatic persistent AF who treated by cryoballoon ablation of the pulmonary veins for 12 months. The two co-primary endpoints of the study focus on the safety of the procedure and efficacy of the procedure in treating AF. The efficacy endpoint is subject to a three-month blanking period in accordance with the current FDA guidance¹.

1

<https://www.fda.gov/medicaldevices/deviceregulationandguidance/guidancedocuments/ucm182016.htm#s6>

The analysis described in this SAP will be conducted by Medtronic statisticians. Efficacy endpoints will be adjudicated by a core lab. Safety endpoints will be adjudicated by the Clinical Event Committee (CEC). Determination of events and event onset dates used in the PMA supplement, PMDA submission, and any resulting publications will be based on the core lab and CEC adjudications. CEC determinations will also be used to determine AE severity and procedure or device-relatedness. Prior to evaluation of the study's primary objectives, a descriptive analysis will be performed. Demographic and other key baseline characteristics will be summarized for the mITT dataset.

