6.2.3.3. Analysis Methods

The probability of a safety event at 12 months (365 days) will be estimated using survival analysis, the Kaplan-Meier method. The standard error will be approximated using Greenwood's formula. A two-sided 95% log-log confidence interval for the probability will be constructed.

For every treated subject, day 0 is defined as the day of the index cryoablation procedure. For subjects with a safety event, the survival date will be set to the date of the safety event. For subjects without a safety event, those subjects will be censored at the last study contact date recorded on CRF which may include the last study visit, the exit date, or death date. If a subject without a safety event is lost to follow-up, the censoring date will be set to the last known study visit date.

For subjects with a repeat ablation within 12 months, the start of the survival analysis will not reset. Day 0 will remain the day of the index cryoablation procedure. Safety events related to the repeat ablation procedure occurring on or prior to 365 days post the index cryoablation procedure will be counted as safety events and count against the primary safety objective. This objective will be analyzed in the mITT dataset: all enrolled subjects who have the Arctic Front Advance Cardiac CryoAblation Catheter inserted into vasculature will be included.

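### Guaranteed Clinical Events Committee review depends on a prior relatedness label, so a listed non-fatal event called unrelated need not be adjudicated; the cryoablation-based definition also does not match the repeat-ablation counting rule.

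*Protocol*

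**What the plan says.** **CEC intake.** CIP section 16 has the committee "review and adjudicate, at a minimum, all system (cryoablation and" one redacted system) "related and all procedure related adverse events, as well as all deaths for subjects participating in the study". CIP sections 12 and 15.5 state the same scope. It is a floor: wider review is allowed but not required.

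**CEC authority.** For the events it reviews, the CEC is responsible for "determining final classifications for all adjudication parameters" (CIP 16), and its classification is the one analysed if the investigator disagrees. SAP 6.2.1 adds that "CEC determinations will also be used to determine AE severity and procedure or device-relatedness".

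**Who labels first.** In CIP Table 10 the investigator and the sponsor each classify relatedness. The visible labels common to both are "Cryoablation procedure related, Cryoablation system related"; one further label is redacted. No section says whose label sends an event to the CEC.

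**What is collected.** CIP 15.2 collects "All Serious Adverse Events (SAEs), regardless of relatedness", together with all procedure-, system- and cardiovascular-related events.

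**The endpoint.** CIP 17.3.2 and SAP 6.2.3.2 require a primary safety event to be serious and to be procedure- or system-related.

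**Definition and counting rule.** CIP Table 9 defines procedure-related as "An Adverse Event directly related to any portion of the procedure that encompasses cryoablation". SAP 6.2.3.3 says: "Safety events related to the repeat ablation procedure occurring on or prior to 365 days post the index cryoablation procedure will be counted". CIP 17.3.2 has the same rule. Neither limits it to cryo repeats.

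**The concern.** Relatedness is one of the two judgements that turn a listed event into a primary safety event. The plan gives the final say on it to an independent committee, and CIP 12 presents that committee as a protection against bias. But the assured route to the committee is set by the same judgement, made earlier by an unblinded investigator or by the sponsor. For a non-fatal event, a label of related can be reviewed and reversed. A label of unrelated need not be reviewed at all, and an event left with that label does not count.

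The trial has a single arm and a fixed 13% limit, so there is no control arm in which the same loss could partly cancel. Any loss of true events moves the observed rate away from the limit.

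The second issue is one of definition. An event caused by a wholly non-cryo repeat procedure is to be counted under one rule, but may not meet the definition of related on which counting depends.

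**Working it through.** **1. Paths through adjudication under the guaranteed scope.**

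| Event as reported | Guaranteed CEC review? | Can it become a primary event? |
|---|---|---|
| Related, serious, listed type | Yes | Yes, or it can be reclassified out |
| Related, not serious | Yes | Yes, if seriousness is upgraded |
| Related, coded as another type | Yes | Yes, if the type is changed |
| Death, any label | Yes | Yes, if found related and within 7 days |
| Non-fatal, listed type, labelled unrelated | No | Only if referred voluntarily |

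The gap is the last row.

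**2. Repeat procedures.** The one repeat permitted in blanking is a cryoballoon PVI (CIP 13.8). Right atrial work with another catheter during it is still part of a procedure that includes cryoablation, so Table 9 covers it. Repeats after blanking are also recorded (CIP Table 7), and left atrial RF is foreseen as an efficacy failure (CIP 13.8). A repeat done wholly without cryo is therefore possible. Its events count under CIP 17.3.2 and SAP 6.2.3.3, but on a literal reading do not meet Table 9.

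**3. The plan's own safety power (SAP 7.2).** Inputs: exact binomial test, one-sided 0.025, goal 13%, true rate 5%. The critical value r is the largest count with P(X ≤ r | n, 0.13) ≤ 0.025; power is P(X ≤ r | n, 0.05).

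- n = 135: r = 9, alpha 0.0141, power 0.860.
- n = 148: r = 11, alpha 0.0233, power 0.932.

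Both match the SAP.

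**4. Events allowed under the planned analysis.** Take 150 treated, no censoring and d events, so S = (150 − d)/150. The log-log upper bound for the event rate is 1 − S^exp(1.96v), where v = √[d/(150(150 − d))] / |ln S|.

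- d = 11: S = 0.9267, v = 0.3016, upper bound 12.85%. Pass.
- d = 12: S = 0.9200, v = 0.2888, upper bound 13.66%. Fail.

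At that boundary, one event that is never referred decides the result.

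**5. Illustration of the loss.** Let m be the share of true endpoint events never labelled related and never referred. The documents give no value, so m is an assumption. The countable rate at a true 13% is 0.13(1 − m), and the chance of passing is P(X ≤ r | n, 0.13(1 − m)).

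| m | Countable rate | n = 150, r = 11 | n = 135, r = 9 |
|---|---|---|---|
| 0 | 13.00% | 2.0% | 1.4% |
| 5% | 12.35% | 3.4% | 2.4% |
| 10% | 11.70% | 5.6% | 3.9% |
| 20% | 10.40% | 13.4% | 9.5% |

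The n = 150 column uses the treated sample and the step 4 limit. The n = 135 column uses the SAP's planning figures; there a 5% loss still stays under 2.5%.

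**6. At the planned rate.** With a true rate of 5%, n = 150 and r = 11, the pass probability is 92.6% with nothing missed and 94.5% with m = 5%. The gap matters chiefly if the true rate is near the limit.

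**The case against.** A reader might infer that only labelled events ever reach the CEC, or that adjudication can remove primary events but never add them. The documents support neither reading. The scope is a minimum, and deaths are reviewed whatever their label. The CEC can add a primary event by upgrading seriousness, changing the event type or finding a death related.

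There are other safeguards. All serious events are collected whatever their relatedness. A sponsor representative reviews every reported event, and the sponsor classifies relatedness as well as the investigator. CIP 16 also lets imaging be requested for serious events with possible relatedness, which is a lower threshold than a firm label. No section says that an investigator's label alone keeps an event from the CEC, and nothing shows that events have been missed.

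On repeats, only a wholly non-cryo procedure is affected. The specific counting rule could fairly be read as overriding the general definition, and the redacted label cannot be checked. The missed shares are assumed, and the inflation figures apply at a true 13%, well above the planned 5%.

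All of this stands, and it limits the claim. It does not close the gap: permission for wider review is not a requirement, the sponsor's label is still a label, and no section refers events by type or timing.

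**Conclusion.** The point holds in limited form. The guaranteed scope provides no way to reverse an unrelated label on a listed non-fatal event, although the SAP gives that decision to the CEC. Separately, Table 9 and the visible Table 10 label need to be reconciled with the repeat-ablation counting rule. How many events either gap would affect cannot be worked out from the documents.

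The size is illustrative. For assumed losses of 5% to 20%, the false-pass chance at a true 13% is 3.4% to 13.4% (n = 150) or 2.4% to 9.5% (n = 135). This assumes that the missed events are never referred by another route and, for n = 150, that there is no censoring. Planned sample size and power are unaffected.

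The change should be made: it removes an avoidable source of bias from a primary endpoint using data and a committee already in place.

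**What to change.** 1. In CIP 15.5 and 16 (and the matching line in CIP 12), refer to the CEC every reported adverse event of a type listed in CIP 17.3.2 with onset in its window after the index or any repeat ablation, whatever relatedness or seriousness label it was given. Seriousness belongs in the rule because it too is part of the endpoint. The windows are those already in the endpoint definition: 7 days for most types and 12 months for pulmonary vein stenosis and atrio-esophageal fistula, with phrenic nerve injury followed to its 12-month status.
2. Align the Table 9 definition of procedure-related, and the corresponding Table 10 label, with the counting rule in CIP 17.3.2 and SAP 6.2.3.3, so that events from any repeat ablation that the analysis counts can be labelled as related.

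The cost is a few more adjudications, a CIP and charter wording change, and possibly a slightly less favourable safety rate. Changing Table 9 also affects which events sites report as procedure-related under CIP 15.2, so site instructions would need the same wording.
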